Guanfacine for PONV and Pain
After Sinus Surgery
Version: March 10, 2016
NCT #: NCT02882854

Principal Investigator: [name]
Assistant Professor
Department of Anesthesiology
Vanderbilt University Medical Center

Department of Anesthesiology
Vanderbilt University Medical Center

Table of Contents:**Study Schema**

- Abstract**
- 1.0 Background**
- 2.0 Rationale and Specific Aims**
- 3.0 Inclusion/Exclusion Criteria**
- 4.0 Enrollment/Randomization**
- 5.0 Study Procedures**
- 6.0 Risks of Investigational Agents (side effects)**
- 7.0 Reporting of Adverse Events or Unanticipated Problems involving Risk to Participants or Others**
- 8.0 Study Withdrawal/Discontinuation**
- 9.0 Privacy/Confidentiality Issues**
- 10.0 Follow-up**
- 11.0 Record Retention**
- 12.0 References**
- 13.0 Testing Regimens**
- 14.0 Data Dictionary**
- 15.0 Patient Data Sheet**

STUDY SCHEMA

| PRE-OP | SURGERY | EMERGE | PACU |
|--------------------|-------------|-----------|----------|
| Consent | Tot GA time | Extubate | Max nVRS |
| Demographics | #pressors | Transport | PONV Tx |
| Study Drug/placebo | | | Max pVAS |
| | | | Total ME |
| | | | PACU LOS |

After meeting I/O criteria pre-operatively, patients will hear a brief description of the study (guanfacine for PONV). If they are interested, potential participants will be given a consent to read and ask questions. After all their questions have been answered, they will sign the consent if they wish to participate. Study drug will be administered with a few sips water. IV pre-med should consist of no more than 2 mg midazolam.

Total time under general anesthesia (induction to extubation) will be recorded along with the number of times pressors are administered. No non-depolarizing muscle relaxant will be administered to avoid the need for reversal agents and the associated confounding factor.

In PACU, the maximum nausea score (nVRS) 0-10 will be recorded, where 0 = none and 10 = maximum, along with the number of times an anti-emetic is required. Maximum pain score (VAS) along with morphine equivalents will also be recorded. PACU length of stay (LOS) will also be recorded. PACU times may be obtained from the PACU records.

Abstract

Postoperative nausea and vomiting (PONV) and post-op pain are the most common problems after all types of surgery and the two major factors delaying post-anesthesia care unit (PACU) discharge. PONV has an incidence of 20-30% if untreated. Pain after surgery is commonly treated with narcotics which can potentiate PONV, further delaying PACU discharge. In multiple studies, alpha-2 agonists such as clonidine and dexmedetomidine reduce both the incidence of PONV and post-op pain, as well as requirements for postoperative analgesics. These actions are mediated via central alpha-2A receptors (A2AR). Of the A2AR agonists, guanfacine (GF), though a weak antihypertensive agent, has the highest selectivity for the A2AR, but to date is untested for its potential to treat either PONV or post-op pain. In this double blind, placebo-controlled study, we will evaluate oral guanfacine versus placebo in patients undergoing sinus surgery for its potential to reduce PONV and pain in the PACU.

Background

Postoperative nausea and vomiting (PONV) and pain are the most common causes of Post Anesthesia Care Unit (PACU) discharge delay, with untreated PONV occurring in 20-30% of post-surgical patients.¹ In addition to the immediate discomfort, patients who suffer with these symptoms may develop maladaptive behavioral changes. Furthermore, managing PONV and pain increases PACU staffing requirements and the direct cost of care.

Because of the published efficacy of alpha-2 agonists in reducing PONV and pain, anesthesiologists at Vanderbilt University Medical Center commonly employ oral, generic off-label guanfacine (GF) pre-operatively with a perceived reduction in these symptoms.

1.0 Rationale and Specific Aims

In efforts to improve the postoperative course of their patients, anesthesiologists have administered several medications with mixed results. Propofol, ketamine, lidocaine, and opioids have been shown to have varying effects in reducing (and sometimes increasing) PONV and pain in the PACU. Over the last few years, alpha-2 adrenergic receptor (A2-AR) agonists have gained popularity as effective agents for reducing these symptoms. By more selectively targeting the A2AR, Dexmedetomidine (DEX) reduces PONV, pain and anxiety with greater hemodynamic stability, but at significantly greater cost. Guanfacine (GF) is the oldest A2-AR agonist in clinical use in this class and the least expensive (10¢/mg). Also, GF is the most highly selective for the

alpha-2A receptor subtype² and the least sedating.³ GFs effects on PONV and pain are unstudied, but it has been used orally for more than 35 years for hypertension, and more than 20 years for managing ADHD.⁴

2.1 PONV

In preventing PONV,⁵ the mechanism of the A2-AR agonists is not perfectly clear, though both CL and DEX have vagolytic, anti-dysrhythmic effects⁶ as well as concomitant anti-sialagogue and airway drying actions. These effects likely arise from brainstem actions at A2-AR in the dorsal motor nucleus of the vagus, the area postrema, and the nucleus tractus solitarius.⁷

2.2 Pain

Both CL and DEX are well studied for pain management, with actions on brainstem and spinal dorsal horn A2-AR. Mechanisms² include a reduction of central sensitization and upregulation of NO synthase.⁸ Furthermore, as a result of the presence and similarity of mu opioid and A2-AR (both Gi/o GPCRs) in locus coeruleus, cross reactivity of the natural ligands at these receptors in LC likely confers (via GIRK channels) the A2-AR descending central analgesic effects.⁹

2.4 Previous Studies

Zhao, *et al.*,¹⁸ recently studied 90 patients, 30/group, undergoing thyroidectomy and receiving intraoperative infusions of either 0.4 or 0.8 mcg/kg/hr DEX vs placebo. The DEX groups had ~1-3-fold lower pain scores (VAS: 0.4 group: 1.50+/-0.52; 0.8 Group: 0.80+/-0.63 vs. Placebo 2.50+/-0.52) in the PACU, as well as a substantially lower incidence of PONV (0.4 Group: 3.3%; 0.8 Group: 0%; Placebo: 13.3%). In a systematic review and meta-analysis of 30 studies of perioperative A2-AR agonist use (aggregate 1,792 pts, 933 receiving DEX or clonidine), Blaudszun *et al.* validated the use of alpha-2 agonists in the reduction of postoperative pain (and reduced opioid requirements) and PONV at one hour, without prolonging PACU times.¹⁹ Tufanogullari *et al.* also showed that dexmedetomidine reduced total morphine equivalents as well as nausea based on an 11-point verbal rating scale (VRS).

The effectiveness of GF in reducing Post-op pain and PONV has never been studied. However, since GF is the most selective A2-AR agonist in clinical use, we believe the reduction of postoperative pain and PONV seen with clonidine and dexmedetomidine can be reproduced (and potentially surpassed) with GF.

2.5 Hypothesis

As a primary endpoint, we hypothesize that patients undergoing a standardized general anesthetic for sinus surgery and are randomized to receive GF vs Placebo will have 20-30% lower PONV scores in PACU, as measured by the 10-point nausea scale (nVRS) previously used in other studies. Secondly, we hypothesize that patients receiving GF will have less pain as measured by visual/verbal analog (VAS) scores and total morphine equivalents (ME) administered in PACU than patients receiving placebo, without significant hemodynamic instability.

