5.0 Study Procedures

5.1 Statistical Analysis and Power

The effect of guanfacine administration on pain and nausea scores will be assessed using proportional odds logistic regression. The odds of greater pain or nausea associated with guanfacine administration will be summarized using the odds ratio and Wald-type 95% confidence interval and Wald test against the null hypothesis of no effect (odds ratio equal to one).

The study design and testing procedure were simulated to study the statistical power. The distribution of pain and nausea scores in the placebo and guanfacine groups were assumed to have the distributions illustrated in the figure below, which correspond to a difference in mean score of 1.5 points, or an (ordinal) odds ratio of 0.25. Taking this as the minimum detectable effect, **80** randomized subjects are needed to achieve 90% power.

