5.42 ANESTHESIA MANAGEMENT

The general anesthetic administered will be standardized as follows:

a. **Premedication:** Midazolam 0 - 2 mg IV

b. **Induction:** Fentanyl: 0.5-2 mcg/kg; Lidocaine: 1-2 mg/kg; Propofol: 1-3 mg/kg; SUX: 0.5-1.5 mg /kg

c. **Maintenance:** with inhalational agent and hydromorphone.

d. **Emergence:** Hydromorphone in 0.25 mg increments as deemed appropriate by anesthesia team and a standardized dose of ondansetron (4 mg) in keeping with routine practice.

5.43 PACU: Hydromorphone for pain and ondansetron for PONV per standardized order set will be administered and documented. IV fluids and oxygen may be continued as long as deemed useful by the PACU and Study staff.

5.5 POST-OP:

A. **PONV** will be quantified by the maximum nVRS.

B. **PAIN** will be evaluated by the maximum Verbal Analog Scale (VAS = 0 – 10: See Fig. 6).

C. **PACU LOS** will be the duration of PACU Length of Stay

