5.6 DATA COLLECTION (See Data Sheet and Data Dictionary)

- A. STANDARD ANESTHESIA PRE-OP ASSESSMENT
- B. ANESTHESIA RECORD COPY
- C. COPY OF SIGNED PATIENT CONSENT FOR STUDY
- D. PATIENT DATA SHEET, (PDS) including Transition Times:**
 - 1. Planned Surgical Procedure, Duration
 - 2. Demographics (age, height, weight, etc.)
 - 3. Nausea score (nVRS) and rescue Tx in PACU
 - 4. Pain Scores (VAS) and Tx in PACU
 - 5. PACU LOS

5.7 STUDY CONDUCT:

5.71 PRE-OP: After soliciting interest and enrolling, **written consent** will be obtained and basic patient data and pre-op assessments (Apfel Score **Fig 2**) performed. Patients will receive GF or placebo orally from a numbered envelope prepared by the IPS in a blinded manner. Patients will then undergo a standardized general anesthetic as described above. At the conclusion of the sinus procedure, patients will be extubated as per routine management and assessed immediately with:

5.72 In PACU, assess the following endpoints:

- A. Max Nausea score (nVRS)
- B. PONV Treatment(s)
- C. VAS (Fig 6): Assess Pain score (Verbal Analog Scale rated 1-10) at 10 and 60 min after PACU arrival
- D. Pain TX: Total Narcotic requirement in PACU (Tallied in Morphine Equivalents for PACU stay)
- E. PACU LOS

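### Does the undefined clause on hemodynamic instability in the second hypothesis need a prespecified measure and comparison?

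*Combined protocol and SAP*

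**What the plan says.** The clause closes the second hypothesis in section 2.5: less pain and fewer morphine equivalents "than patients receiving placebo, without significant hemodynamic instability". Nothing there defines the last words.

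Other places bear on it:

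- **Rationale (section 1.0) and Abstract.** Dexmedetomidine, through more selective receptor targeting, is said to be an agent that "reduces PONV, pain and anxiety with greater hemodynamic stability, but at significantly greater cost". Guanfacine is described as an agent that, "though a weak antihypertensive agent, has the highest selectivity for the A2AR".
- **Study Schema.** Total anesthesia time is recorded "along with the number of times pressors are administered".
- **Section 5.1.** The stated analysis is limited to two scores: "The effect of guanfacine administration on pain and nausea scores will be assessed using proportional odds logistic regression".
- **Sections 5.5 and 5.72.** PONV "will be quantified by the maximum nVRS". The list headed "In PACU, assess the following endpoints" holds nausea, its treatment, pain, opioid use and length of stay. Neither section names blood pressure or heart rate.
- **Section 5.6.** Item B of the data to be kept is "ANESTHESIA RECORD COPY".
- **Sections 6.0 and 7.0.** Modest hypotension is named as a drug risk, and unexplained vital-sign changes are an example of an adverse event to be reported to the IRB.

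The Data Dictionary says the Patient Data Sheet carries everything collected on each patient. The contents list that sheet as section 15.0, but it is not in the text available for review.

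**The concern.** A hypothesis that promises an effect without harm has two halves, and here only the efficacy half has a measure and a model. The drug is an antihypertensive, the protocol names hypotension as a risk, and the rationale trades on selectivity and stability. Readers will therefore look for a result on the clause.

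If the measure is chosen from the anesthesia record after unblinding, a real fall in blood pressure could be presented as no significant instability by picking whichever measure or cut-off has an interval that includes zero. Adverse-event reporting does not close the gap: it has no threshold and makes no comparison by arm, and an expected drug effect might not count as unexplained.

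**Working it through.** The plan gives no hemodynamic figure to reproduce. There are three checks: what the text supplies, how much a prespecified comparison could deliver, and whether leaving the measure open is as costly as it looks.

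**1. What the text supplies**

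| Need | Present in the supplied text? |
|---|---|
| Intraoperative measure | Yes: pressor count (schema) |
| Intraoperative source record | Yes: anesthesia record copy (5.6 B) |
| Named blood pressure or heart-rate variable | None seen; the 15.0 form cannot be checked |
| PACU hemodynamic variable | None seen; same limit |
| Stated analysis by arm | No |

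The last row is not peculiar to hemodynamics. Section 5.1 also gives no analysis for morphine equivalents, which stand in the same sentence of 2.5, or for PACU length of stay.

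**2. What 40 per arm can deliver**

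Input: n = 40 per arm (5.2). Event rates and margins are assumptions, because the documents give none.

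- *No events in an arm.* The exact two-sided 95% upper limit is 1 − 0.025^(1/40) = 8.8%.
- *Difference in proportions, equal counts.* The Newcombe half-width is √[(p − l)² + (u − p)²], where l and u are the Wilson limits. For 4/40, l = 0.040 and u = 0.231, so √(0.060² + 0.131²) ≈ 0.144. In the same way, 8/40 gives 0.176, 12/40 gives 0.195 and 20/40 gives 0.209.
- *Lowest blood pressure as a mean difference.* The half-width is t(0.975, 78) × √(2/40) = 0.445 SD, or about 4.5 to 8.9 mmHg for an assumed SD of 10 to 20 mmHg.
- *Patients needed to rule out a 10-point excess* (one-sided 0.025, 80% power, equal true rates): n per arm = (1.960 + 0.842)² × 2p(1 − p)/0.10².
  - p = 10%: 7.85 × 0.18/0.01 ≈ 142
  - p = 20%: 7.85 × 0.32/0.01 ≈ 252
  - p = 30%: 7.85 × 0.42/0.01 ≈ 330

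With a 20-point margin the need falls to 36, 63 and 83 per arm, so 40 would suffice only at the lowest rate and the widest margin.

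**3. The cost of leaving the measure open**

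Simulation assumptions: 40 per arm; normal lowest blood pressure with SD 1; guanfacine lower by 0.5 SD. The four candidate measures are the mean difference (t interval) and the proportion below the placebo 10th, 20th or 30th percentile (Newcombe interval).

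| Measure reported | 95% interval includes zero |
|---|---|
| Mean difference, fixed in advance | 40% |
| Below 10th percentile, fixed in advance | 70% |
| Below 20th percentile, fixed in advance | about 63% |
| Below 30th percentile, fixed in advance | about 58% |
| At least one of the four | 83% |

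The contrast of 40% with 83% is 43 points. A cut-off at the 10th percentile, fixed in advance and used alone, already accounts for 70 − 40 = 30 of them with no selection at all. Selection adds 83 − 70 = 13 over that choice, or 83 − 58 = 25 over the 30th-percentile cut-off. The pattern is the same for other shifts. At 0.3 SD the mean difference gives 73%, the 10th-percentile cut-off alone 88%, and at least one of four 96%. At 0.7 SD the figures are 13%, 44% and 57%.

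**The case for a change.** The strongest case for a change is that a stated hypothesis clause has no comparison fixed in advance, and that repair is cheap. Five abstracted fields for 80 patients come to 5 × 80 = 400 values, or 3 × 80 = 240 for the operating room alone, plus one descriptive table. No new assessment of patients is needed. A retained source record is not a variable and leaves the analyst free to choose. The anesthesia record also does not reach into PACU. Morphine equivalents and length of stay lack an analysis too, but they are at least named outcomes in 5.72.

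Much of this stands. The clause is undefined, the pressor count has no stated analysis, and choosing a measure after unblinding is a real hazard: with no true effect, at least one of the four intervals excludes zero in about 13% of trials instead of 5%.

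Three things weaken the call for a change. First, adding lowest blood pressure would still leave open whether it is systolic or mean, how baseline is handled, and what to do about readings already altered by pressors. Secondly, because the 15.0 form is not available, it cannot be said that vital signs go uncollected. Thirdly, the at-least-one figures suppose an analyst who always reports the most favourable of four results.

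**Conclusion.** No change to the plan follows. This is missing detail attached to a subordinate clause. It contradicts no stated rule or number, and the primary nausea analysis, the pain analysis and the sample size do not depend on it.

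An analyst can fill the gap in the ordinary way, with pressor use and blood pressure by arm from data the protocol already captures, presented as description. Formal prespecification would buy little. At about ±14 to ±21 points for a proportion, or ±0.445 SD for a mean, 40 per arm gives an estimate with a wide interval and could not establish absence of instability, however the measure was defined. The clause can be read only as an expectation, and a report that described it as demonstrated would overreach.

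The precision figures rest on assumed event rates of 10% to 50%, and the simulation on assumed shifts and cut-offs. The textual conclusion depends on neither. It is limited by the absence of the 15.0 data sheet from the text reviewed.

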3.0 Inclusion/Exclusion Criteria

3.1 Inclusion Criteria

- VUMC patients undergoing sinus surgery in MCE OR.
- Adults aged 18 and older

3.2 Exclusion Criteria

- Patients who do not meet the inclusion criteria
- Inability to read and freely consent
- Patients who take alpha-2 agonists routinely (guanfacine, clonidine, tizanidine)
- Patients undergoing sinus surgery planned for greater than 3 hours
- Patients with significant pre-existing pain, on chronic pain (opioid, methadone) therapy, severe fibromyalgia or other pre-existing pain condition in any body part
- Patients with pre-op nausea/vomiting at baseline.
- Pregnant or lactating women.

4.0 Enrollment

[figure not shown]
Patients identified as candidates by primary criteria (above inclusion/exclusion listing) will be interviewed immediately prior to surgery to determine suitability and patient willingness to participate in the study. After receiving complete information and a description of the study, patients accessioned will give written consent. On pre-op administration, Pt. Name, MRN and Study Drug Envelope Number (SDE#) will be logged into the Study Database in REDCap and reported directly to IPS with a completed Study Drug Administration Sheet, either by hand or by FAX.

5.0 Study Procedures

5.1 Statistical Analysis and Power

The effect of guanfacine administration on pain and nausea scores will be assessed using proportional odds logistic regression. The odds of greater pain or nausea associated with guanfacine administration will be summarized using the odds ratio and Wald-type 95% confidence interval and Wald test against the null hypothesis of no effect (odds ratio equal to one).

The study design and testing procedure were simulated to study the statistical power. The distribution of pain and nausea scores in the placebo and guanfacine groups were assumed to have the distributions illustrated in the figure below, which correspond to a difference in mean score of 1.5 points, or an (ordinal) odds ratio of 0.25. Taking this as the minimum detectable effect, **80** randomized subjects are needed to achieve 90% power.

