5.2 RANDOMIZATION

Subjects will be randomized to one of TWO GROUPS: **Group A:** Forty (40) patients will receive GF 1 mg orally; OR, **Group B:** Forty (40) patients will receive a similar appearing placebo (containing no drug) from numbered study drug envelopes (SDE) prepared by Vanderbilt's Investigational Pharmacy Service (IPS) which will independently randomize the drug envelopes and maintain the Master Drug Study Log.

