8.0 Study Withdrawal/Discontinuation

8.1 Withdrawal. After Study Drug administration, this study involves only assessment for nausea and vomiting (nVRS) and pain (VAS) in the surgical setting of sinus surgery. After patients have been enrolled and consented, it is not anticipated that patients will voluntarily withdraw. Nevertheless, patients are free to withdraw at any time, simply by telling one of the study physicians/managers. However, after enrollment and initial pre-op study assessment, patients may withdraw up to the point of anesthetic induction and surgical procedure, and thereafter, may only withdraw when fully awake and alert in PACU.

8.2 Discontinuation. This study is designed as intention-to-treat, so once subjects have taken the Study Drug, they will be followed per protocol through completion, or up to any time they choose to withdraw or any unspecified Adverse Event that would halt normal data collection. In either event, data obtained to that point in the protocol would be included in the total dataset, with reporting of the withdrawal or AE as noted above.

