13.0 Testing Regimens

Fig 3. Verbal/Visual Analog Pain Score (VAS) ²⁹:

NO PAIN ----- WORST PAIN
 0-----1-----2-----3-----4-----5-----6-----7-----8-----9-----10

At 10, 30, and 60 min after PACU arrival ask patient to verbally score their pain on this scale.

Data Dictionary-

1. Patient Data Sheet, (PDS) will include all data collected on each individual:

A. Planned Surgical Procedure (all sinus surgeries not greater than 3 hours)

B. Demographics: Data identifying characteristics of each patient, including

Age, Gender, Height, Weight, MRN, etc.)

2. POST-OP:

A. Anesthetic Duration – Difference between induction and extubation recorded in the Anesthesia Record; PACU Entry Time

B. PONV will be quantified by a Nausea Verbal Reporting Scale (nVRS), 0-10

C. PAIN will be evaluated by Verbal Analog Scale (VAS = 0 – 10). (See Fig. 3)

D. PACU LOS

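### The primary nausea model names no covariate although the Apfel PONV risk score is assessed before dosing: a modest, conditional efficiency gain, not an error

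*Combined protocol and SAP*

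**What the plan says.** - **Primary endpoint.** Section 2.5 makes the PACU nausea score primary: "As a primary endpoint, we hypothesize that patients undergoing a standardized general anesthetic for sinus surgery" and so on. Section 5.5 takes the maximum nVRS.
- **Model.** Section 5.1: "The effect of guanfacine administration on pain and nausea scores will be assessed using proportional odds logistic regression". The result is an odds ratio with a Wald 95% interval and a Wald test. No covariate is named, and the section does not say whether the model is adjusted.
- **Planning effect.** The assumed score distributions are those "which correspond to a difference in mean score of 1.5 points, or an (ordinal) odds ratio of 0.25", giving 80 subjects for 90% power.
- **Randomisation.** Section 5.2 puts 40 in each arm by numbered envelopes from the pharmacy, "which will independently randomize the drug envelopes and maintain the Master Drug Study Log". No stratification factor is stated.
- **Baseline risk score.** Section 5.71 lists "basic patient data and pre-op assessments (Apfel Score" among the steps before study drug. Reference 28 is titled as a risk score for predicting PONV. No section gives the score a role in analysis or allocation.
- **Data items.** Section 5.6 has "Demographics (age, height, weight, etc" but does not name the Apfel score; nor does the data dictionary.

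**The concern.** The trial assesses, before dosing, a score built to predict the condition that its primary endpoint measures, and then gives it no stated use. In a non-linear model such as proportional odds, leaving out a prognostic baseline variable pulls the treatment odds ratio towards one and costs some power. With 40 per arm and no stated stratification, the arms can also differ by chance in baseline risk, and an unadjusted result from the single trial then depends on which way they differ. Because section 5.1 is silent on covariates, the choice of model is also not fixed in advance.

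**Working it through.** **Inputs from the documents:** 40 per arm; ordinal odds ratio (OR) 0.25; mean difference 1.5 points; 90% power; Wald test. A two-sided 5% level is inferred from the 95% interval.

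**Assumptions, because the documents give no figure:** the placebo nausea distribution (the figure in section 5.1 is not in the supplied text), an Apfel range of 0 to 4, the mix of scores, and the OR for nausea per Apfel point (1.0, 1.5, 2.0 or 2.5).

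**1. The plan's own figure.** Whitehead's formula is N = 12(z₀.₉₇₅ + z₀.₉₀)² / [(ln OR)²(1 − Σp̄³)], where p̄ are the category proportions averaged over arms.

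- With OR 0.25: 12 × 3.2415² / 1.3863² = 65.6, so N = 65.6 / (1 − Σp̄³). N = 80 needs 1 − Σp̄³ = 0.820.
- A placebo distribution with 40% at 0 and a geometric tail (ratio 0.8) gives a mean difference of 1.46, 1 − Σp̄³ = 0.818 and N = 80.2.
- Other assumed shapes with mean differences of 1.4 to 1.6 give N from about 70 to 107.

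So 80 is attainable and not contradicted, but cannot be strictly reproduced without the figure.

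**2. Power with and without the score.** Each run simulated 40 per arm and entered the score linearly.

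- Run A: 8,000 trials per scenario; Apfel mix 8/25/34/25/8%; tail ratio 0.814 (40% at 0) or 0.741 (20% at 0); conditional effect solved so that the large-sample unadjusted OR is 0.25. Monte Carlo standard error is about 0.35 points.
- Run B: 3,000 trials; mix 10/25/30/25/10%; tail ratio 0.8; average marginal log OR set to ln 0.25. Standard error is about 0.6 points.
- Run C: a further 3,000 trials.

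Power in %, unadjusted → adjusted (change in points), by assumed OR per Apfel point:

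| Run | 1.0 | 1.5 | 2.0 | 2.5 |
|---|---|---|---|---|
| A, 40% at 0 | 88.2 → 87.9 (−0.3) | 88.6 → 90.2 (+1.6) | 88.4 → 92.2 (+3.8) | 89.1 → 94.3 (+5.2) |
| A, 20% at 0 | 92.3 → 92.2 (−0.1) | 92.4 → 93.7 (+1.3) | 93.0 → 96.3 (+3.3) | 92.8 → 97.3 (+4.5) |
| B, 40% at 0 | 88.7 → 88.7 (about 0) | 87.9 → 90.1 (+2.2) | 87.3 → 92.0 (+4.7) | 86.7 → 93.9 (+7.2) |
| C, 40% at 0 | 88.0 → 88.0 (0.0) | 88.7 → 89.3 (+0.6) | 88.2 → 91.9 (+3.7) | 89.2 → 95.0 (+5.8) |

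In run B the unadjusted power itself drifts down as the score strengthens, so 7.2 is the top edge of the range.

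**3. Where the gain comes from.** It is not a narrower interval. In run A (40% at 0), effect over median standard error is:

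- unadjusted: |ln 0.250| / 0.46 = 1.386 / 0.46 = 3.01;
- adjusted, OR per point 1.5: |ln 0.237| / 0.47 = 1.440 / 0.47 = 3.06;
- adjusted, 2.0: |ln 0.215| / 0.49 = 1.537 / 0.49 = 3.14;
- adjusted, 2.5: |ln 0.194| / 0.50 = 1.640 / 0.50 = 3.28.

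The standard error rises, but the conditional log OR moves further from zero.

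**4. Chance imbalance.** The run A mix has variance 2(0.08 × 4 + 0.25 × 1) = 1.14, so the between-arm difference in mean Apfel has SD √(2 × 1.14 / 40) = 0.24. About 16% of trials lie beyond one SD on each side. Power in those tails (40% at 0; OR per point 1.5 / 2.0 / 2.5; error about 1 point):

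- guanfacine arm at higher risk: unadjusted 80.3 / 77.5 / 75.4%, adjusted 88.7 / 92.3 / 94.6%;
- guanfacine arm at lower risk: unadjusted 94.8 / 96.4 / 97.6%, adjusted 90.3 / 91.5 / 93.3%.

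These tails are already averaged into the table above. Overall type I error is 4.7 to 5.3% unadjusted and 5.1 to 5.7% adjusted.

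**5. Missing scores.** With 10% missing at random (assumed; run A, 40% at 0), dropping those patients gives adjusted power of 84.5 / 87.1 / 88.9 / 91.8% at 1.0 / 1.5 / 2.0 / 2.5. That is below the unadjusted test at 1.0 and 1.5. Imputing the overall mean gives 88.1 / 89.9 / 91.8 / 93.9%.

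**The case against.** The strongest reply is that nothing here is wrong. Randomisation makes the unadjusted test valid, and the gain depends on a prognostic strength that no section states. The population is narrow (one type of surgery, preoperative nausea excluded, ondansetron for all at emergence), so nothing favours the strong end of the range. All of this stands.

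Four stronger readings are tempting, and the documents do not support them:

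- *The plan forfeits several points of power.* That needs an odds ratio near 2 per Apfel point. At 1.5 the gain is about 0.5 to 2 points.
- *The plan has chosen an unadjusted analysis.* Section 5.1 names no covariate but does not rule one out. The supportable statement is that covariates are unspecified.
- *Chance imbalance is a further harm.* The two tails offset each other and are already in the average. What adjustment adds is that the one trial actually run depends less on which tail it falls in.
- *The score may not be recorded.* Section 5.71 requires the assessment, section 5.6 includes the standard preoperative assessment, and the data dictionary says "Patient Data Sheet, (PDS) will include all data collected on each individual". The data sheet itself (15.0 in the contents) is not in the supplied text, so non-capture cannot be inferred.

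What survives is a low-cost change that uses a baseline value the trial already assesses, with no material loss if the score turns out not to be prognostic.

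**Conclusion.** The point holds as an efficiency and pre-specification matter. At 40 per arm and a marginal odds ratio of 0.25, adjustment changes power by about 0 points if the Apfel score is not prognostic, about +0.5 to 2 points at 1.5 per Apfel point, and about +3 to 7 points at 2.0 to 2.5. These sizes rest on the assumed nausea distributions, Apfel range and mix, and prognostic strength. The direction is consistent across all runs. A reader should not infer that the planned test is invalid, that 80 is too few, or that adjustment would narrow the interval.

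**What to change.** Before unblinding:

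1. State in section 5.1 that the primary nausea model contains treatment plus Apfel score (linear, 1 df), with the unadjusted model as supportive. The latter estimates the marginal odds ratio used for planning.
2. State that the primary odds ratio is conditional on Apfel score.
3. Name the Apfel score in section 5.6 and in the data dictionary, as a model covariate should be.
4. Impute a missing score with the overall baseline mean, blind to arm, so that no randomised patient is dropped. Section 8.2 says: "This study is designed as intention-to-treat, so once subjects have taken the Study Drug, they will be followed per protocol through completion".

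The cost is one model term and one named baseline item. When the marginal odds ratio is 0.25, the primary one becomes about 0.24, 0.22 or 0.19 at assumed odds ratios per point of 1.5, 2.0 or 2.5, with a slightly larger log-scale standard error. In trials where chance imbalance favours guanfacine, adjusted power is about 4 to 5 points lower than unadjusted (run A, 40% at 0).
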